3. Participation in a new study evaluating anti-resorptive therapy for prevention of bone loss after stopping TPTD. The new study is currently in the design phase and funding phase and precise details are not yet available

All currently enrolled subjects would be re-consented and future participants would sign a new informed consent document with the new study design.

On January 26, 2014, the Research Pharmacy informed the Principal Investigator that there was a mistake in the randomization table for the study. Subjects (n=40) should have been randomized 28:12, active Teriparatide to placebo, for 6 months, followed by a single-switchover design in which all would receive active drug. The randomization code in the table provided to the Research Pharmacy by the Study Statistician was reversed and the subjects were randomized 12:28, active Teriparatide to placebo. To date, 18 patients have been enrolled and randomized. Research Pharmacy has informed us that 12 subjects were randomized to placebo and 6 to active Teriparatide. As 12 subjects have already been randomized to receive placebo first, we will increase enrollment by one subject (total, 41) and generate an adaptive randomization table in which one of the 23 subjects yet to be enrolled will be randomly assigned to placebo and 22 will be randomly assigned to active Teriparatide. This will maintain the number of subjects treated with active drug at 28 and maintain blinding of subjects and study personnel to study assignment.

2. Study Design and Statistical Procedures

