Prior to statistical analysis, all outcome and covariate data will be summarized with descriptive statistics, outliers examined, distributions identified and normalizing transformations applied where indicated. All of the above analyses will be based upon the intention-to-treat principle. The missing data mechanism (MCAR, MAR) for all outcomes and covariates will be assessed and, in the event of a non-ignorable mechanism, analyses will subjected to the methods of Diggle and Kenward³⁹ for continuous measures or Ibrahim and Lipsitz⁴⁰ for safety outcomes. Bone turnover markers will be log-transformed prior to analysis. Inferential testing will use a 5% two-tailed type I error rate with no adjustment for multiplicity taken for primary outcome analyses. Secondary efficacy analyses type I error rates will be adjusted by Bonferroni method whereas secondary safety analyses will not. In keeping with the objective of proposed exploratory analyses to generate data patterns consistent or inconsistent with improved bone quality, no adjustment for multiplicity will be taken. No interim efficacy analyses are planned. The statistical analysis plan will be modified to account for the adaptive randomization procedure, which is relevant to Aim 1 only.

AIM 1:

Primary efficacy outcome analysis: Analysis of covariance (ANCOVA) comparison of between-group (treated vs placebo) differences in mean change in LS aBMD (g/cm^2) by DXA from pre-treated baseline to 6 months of assigned treatment with adjustment for the following continuous baseline variables LS aBMD (g/cm^2), age (years) and weight (kg).

Primary safety outcome analysis: Fisher's Exact test of between-group difference in the number of people in each assigned group reporting at least one hypercalcemia or hypercalciuria event in the first 6 months of assigned treatment; followed by Cox proportional hazards model analysis of the between-group difference in the time-to-first hypercalcemia or hypercalciuria event; followed by GEE testing of the between-group difference in the temporal pattern of the repeatedly sampled hypercalcemia or hypercalciuria events in the first 6 months of assigned treatment.

Secondary efficacy outcome analyses: TH, FN and 1/3 Radius aBMD by DXA will analyzed by ANCOVA as described for the primary outcome, above.

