Primary efficacy outcome analysis: Analysis by linear mixed models for repeated measures (LMM_R) of the within-group (TPTD) change in LS aBMD (g/cm²) by DXA from pre-treatment baseline with repeated measures at 12- and 24-months. (This is a growth curve model testing the hypothesis that the temporal trajectory of within-subject change in outcome differs from a random process.) The model estimates the fixed effect of time, random effects for subject, error and the quadratic and cubic values of time entered as random effects, continuous covariates for age and weight at baseline and with an AR(1) covariance structure. The random effects for higher-order factors for time model monotonic and U-shaped components of the growth curve. Model estimated within-subject differences between specific timepoints will be assessed when the fixed effect of time is statistically significant. The LMM_R model will be repeated for LS trabecular vBMD by cQCT after 24 months of teriparatide. Secondary efficacy outcome analysis: The same LMM_R analysis proposed for Aim 2 primary outcomes

will be used for secondary efficacy outcomes of TH, FN and $1/3^{rd}$ RD aBMD by DXA and HRpQCT after 12 and 24 months, and cQCT after 24 months of TPTD. These analyses will also be used to explore the pattern of change in serum BTMs (P1NP and CTx), between baseline and 24 months. Exploratory analyses will also be conducted to determine whether clinical factors such as age, BMI, body composition, and aspects of the growth hormone axis may predict BMD response to TPTD.

2.B. Power and Sample Size

We have based our power calculations upon the preliminary data generated from our recent pilot study of 22 women with IOP who were treated with teriparatide for 24 months. Our power estimates are based upon 40 women randomized to TPTD or placebo (28:12) with data for analysis, assuming a 10% drop-out and an alpha level of 5%.

AIM 1:

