Primary efficacy outcome: For the primary endpoint of between-group difference in LS BMD at 6 months, power calculation assuming the proposed two-group ANCOVA and outcome correlation with baseline covariates of 0.3, we will have >90% power to detect a difference of $3.7 \pm 3.3\%$ in the TPTD-treated vs. $0.8 \pm 2.9\%$ in the placebo-treated group (placebo estimate based on interpolation from our preliminary data at 12 months). The estimated effect size is consistent with an annual TPTD-induced increases of 7.0-13.5% in studies by Arlot et al. in postmenopausal women, Langdahl et al. in premenopausal women with GIOP, and Kurland et al. in male IOP³⁶.

Primary safety outcome: For our primary safety outcome, the between-group difference in the number of people in each assigned group reporting at least one hypercalcemia or hypercalciuria event, we do not expect to have sufficient power to detect group differences in event rate because of the rarity of TPTD-related safety events observed in our pilot study and reported by others in the literature. Secondary efficacy outcome: For our secondary efficacy endpoints of between-group differences in TH, FN and 1/3R, our preliminary data suggest that we will not have sufficient power to detect between groups differences in these measures at 6 months, as the increases are less pronounced than at the LS. Secondary safety outcome: While we will closely examine the safety data, our small sample size provides minimal power to detect any but the most dramatic differences in safety profile between groups.

AIM 2:

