Primary efficacy outcomes: For MdPm and BFR/BS after 3 months of TPTD, we base our effect size assumptions on the Lindsay et al²⁸ estimates of changes from baseline to 1-month of cyclic TPTD treatment (assuming these measures are virtually unchanged over 3 months in the placebo treated group). Lindsay reports cancellous BFR/BS increased from 0.008 ± 0.006 to 0.027 ± 0.018 (a standardized effect size of 1.42) and cancellous MdPm from 1.33 ± 0.95 to 3.78 ± 2.53 after 1 month (a standardized effect size of 1.28). With the proposed sample size, we will have over 90% power to detect difference comparable or larger than the increase in bone formation detected by Lindsay after 1-month of treatment. Secondary analyses to assess the predictability of DXA and cQCT changes from baseline and 3-month changes in BFR/BS and MdPm: The proposed sample size enables us to detect between 40% to 55% of the variance accounted for in the 12- or 24-month DXA or cQCT change and the baseline to 3-month change in BFR/BS or MdPm (assuming 80% power, 5% alpha and a multiple regression model with up to 3 covariates partialled from both the bone density outcome and the histomorphometric predictor).

AIM 3:

Primary efficacy outcomes: For LS aBMD by DXA after 12 and 24 months of TPTD, we will have >86% power to detect changes from baseline. We based our estimate of LS aBMD at 12 months on our preliminary data, and at 24 months on the data of Graeff et al.⁴¹ who detected a 10.2% increase in aBMD over 24 months. We anticipate that the increase between baseline and 12 months will far exceed the increase from 12 to 24 months, which may not be statistically significant. For trabecular vBMD at the spine by cQCT after 24 months of TPTD, the work of Rehman et al.³², who detected an increase of 35% in vBMD, suggests that we will have power of >99% to detect within-group changes.

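### Section 2.B states over 90% power for Aim 1 from one concurrent 28:12 randomization. Under the amended 6:12 then 22:1 allocation, an analysis that accounts for the change has about 54-56%.

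*Combined protocol and SAP*

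**What the plan says.** Section 2.B sets the basis for all power statements: "Our power estimates are based upon 40 women randomized to TPTD or placebo (28:12) with data for analysis, assuming a 10% drop-out". For the Aim 1 primary endpoint it assumes an "outcome correlation with baseline covariates of 0.3" and claims "we will have >90% power to detect a difference of" 3.7% (SD 3.3) on teriparatide against 0.8% (SD 2.9) on placebo. Section 2.A sets the error rate: "Inferential testing will use a 5% two-tailed type I error rate with no adjustment for multiplicity taken for primary outcome analyses".

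The end of Section 1 reports that the randomization table had been reversed. Of the 18 women randomized by then, 6 were on teriparatide and 12 on placebo. For the rest, "one of the 23 subjects yet to be enrolled will be randomly assigned to placebo and 22 will be randomly assigned to active Teriparatide". The Section 2 design paragraph and the Visit 3 description carry only the totals, 28 and 13.

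Section 2.A adds: "The statistical analysis plan will be modified to account for the adaptive randomization procedure, which is relevant to Aim 1 only". The modification itself does not appear. The Aim 1 ANCOVA adjusts for baseline lumbar spine BMD, age and weight, and the Aim 2 ANCOVA for age and weight. Neither has a term for randomization period. For Aim 2, Section 2.B says "With the proposed sample size, we will have over 90% power to detect difference comparable or larger than the increase in bone formation detected" in an earlier labelling study, with standardized effects of 1.42 (BFR/BS) and 1.28 (MdPm).

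**The concern.** When the allocation changes from 1:2 to 22:1, treatment becomes closely tied to time of enrolment. Twelve of the 13 placebo women come from the first 18 enrolled, and 22 of the 28 teriparatide women come from the last 23. Only comparisons within a period are protected by randomization, and the second period has a single placebo woman. Adding a 41st subject keeps 28 women on active drug first, as Section 1 intends, but it does not keep the power.

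The power printed in Section 2.B therefore belongs to a different design from the one being run. A non-significant primary result would be read against more than 90% power, although the randomization-respecting comparison has little better than even odds of detecting the assumed effect. The team also has no planning figure showing how much depends on one second-period placebo woman.

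**Working it through.** **Inputs.** Two-sided 5% (Section 2.A). Difference 3.7 - 0.8 = 2.9 points, SDs 3.3 and 2.9, correlation 0.3 (Section 2.B). Allocation 28:12 (Section 2.B), 6:12 then 22:1 (Section 1).

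**Formulas.** Information on the treatment contrast is n1 x n0/(n1 + n0), summed over periods when the comparison is made within period. Power comes from the noncentral t with noncentrality d x sqrt(information), where d = 2.9/(SD x sqrt(1 - 0.3^2)). The common SD is 3.19 (weighted by n) or 3.11 (equal weights), so d = 0.95 or 0.98. Each pair below follows that order.

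**Information**
- 28:12 as in Section 2.B: 28 x 12/40 = 8.40
- Concurrent 28:13: 28 x 13/41 = 8.88
- Within period: 6 x 12/18 + 22 x 1/23 = 4.00 + 0.96 = 4.96

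The within-period figure is 4.96/8.40 = 59% of the Section 2.B basis and 4.96/8.88 = 56% of a concurrent 28:13. It matches a 28:12 trial of about 0.59 x 40 = 24 women. The last 23 women (56% of 41) supply 0.96/4.96 = 19% of it.

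**Aim 1 power (stated: over 90%)**

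| Analysis | Information | Power |
|---|---|---|
| 28:12, as in Section 2.B | 8.40 | 77%, 79% |
| 28:13, no period term | 8.88 | 79%, 81% |
| Within period | 4.96 | 54%, 56% |
| Within period, 10% drop-out | 4.46 | 50%, 52% |

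The stated figure does not reproduce at 28:12. It is reached only if covariates explain about 27-30% of the variance, the SDs are treated as unequal and there is no further drop-out. By normal approximation with SD 3.19, 90% power needs information of (1.960 + 1.282)^2/0.953^2 = 11.6, more than any of these designs supplies.

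**Sensitivity of the within-period figure**
- Reading 0.3 as R-squared: about 65-70%, depending on SD and approximation.
- A linear enrolment-order term in place of a period term: averaged over random orderings, information is just under 6 and power about 62%.
- Simulation: 51% with a period term in the ANCOVA (4,000 trials) and 47% with a re-randomization test (800 trials).

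**Fragility.** Losing one first-period placebo woman changes information from 4.96 to 6 x 11/17 + 0.96 = 4.84. Losing the only second-period placebo woman takes it to 4.00 and Aim 1 power to about 46%.

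**Aim 2.** At 28:12 the printed effect sizes give 98% (BFR/BS) and 95% (MdPm), so the stated power reproduces. With the ANCOVA as written at 28:13 the figures are 98% and 96%. If period were accounted for:
- Period term: 87% and 79% (83% and 75% with 10% drop-out).
- Linear enrolment-order term: about 92% and 86%.
- Simulated ANCOVA on change with a period term, arm-specific SDs and an assumed within-woman correlation of 0.3: 80% and 69%.

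**The case against.** Four points can fairly be made against this.

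First, Section 2.A names no method, so a strict within-period comparison is one choice among several. This stands. Adjusting for enrolment order is an ordinary alternative and loses less information. It still leaves Aim 1 at about 62%, so the conclusion for Aim 1 does not depend on the choice.

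Second, a reader might infer that Aim 2 also loses its stated power. The documents do not support that. Section 2.A confines the modification to Aim 1, and the Aim 2 ANCOVA as written stays above 90%. Even with an adjustment, BFR/BS ranges from below to just above 90% by method. What remains is a question of consistency: the Aim 2 primary analysis is also a between-group comparison of the same randomized women, so the restriction needs a reason.

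Third, a reader might infer that the amendment alone removed the Aim 1 power, or that more than 90% was right for the original design. On the plain reading of 0.3 as a correlation it was not: 28:12 gave 77-79%. The amendment costs roughly a further 23 points.

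Fourth, Section 1 calls the study exploratory and disclaims labelling claims. That limits the consequences, but Aim 1 remains the primary efficacy comparison and its stated power should describe the design being run.

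**Conclusion.** The point holds for Aim 1. Section 2.B prints more than 90% power from a single 28:12 randomization that the trial no longer has. An analysis accounting for the change, as Section 2.A promises, has about 54-56% power on the printed inputs. It stays below 90% under every reading tried, with about 70% the highest.

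This assumes that accounting for the procedure means a period term, within-period re-randomization or an enrolment-order term, since the documents do not say which. It is also unclear whether the 40 women already allow for the 10% drop-out, so figures with and without it are given.

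For Aim 2 there is no power error as the analysis is written. There is an unreconciled restriction, and any power under a period adjustment depends on the method.

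**What to change.** In Section 2.B, replace the 40-woman 28:12 basis with the actual allocation: 6:12, then 22:1, 41 women. Write the Aim 1 modification that Section 2.A promises, naming the method, before the Aim 1 data are analysed. Then:

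- State Aim 1 power for that analysis with its assumptions: about 54-56% with a period term (50-52% with 10% drop-out), or about 62% with a linear enrolment-order term.
- Give the unadjusted 28:13 figure (about 79-81%) beside it, labelled as partly non-concurrent.
- Do not say that more than 90% applied to Aim 1 at 28:12.
- Note that the single second-period placebo woman carries about 19% of the within-period information.
- In Section 2.A, either justify confining the modification to Aim 1 or extend it to the Aim 2 primary analysis. If extended, report Aim 2 power as conditional on method: about 83-92% for BFR/BS and 75-86% for MdPm at the printed effect sizes, and about 80% and 69% in the simulation with arm-specific SDs.

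The cost is wording, recalculation and a less favourable stated power. No additional women, visits or procedures are needed.

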randomized, double blind, placebo-controlled, single switch-over trial of TPTD in premenopausal women with IOP. Forty-one subjects will be assigned to TPTD (Group A; n=28) or placebo (Group B; n=13). At the 6 month timepoint, all subjects will receive TPTD, but blinding of original group assignment will be maintained for an additional 6 months. At the 12 month visit, the blind will be broken and those initially randomized to TPTD (Group A) will continue on study drug for an additional 12 months while those initially randomized to placebo (Group B) will continue for an additional 18 months, so that subjects in both groups complete 24 months of treatment overall. aBMD by DXA and HRpQCT will be measured at baseline and at 6 month intervals. vBMD by cQCT will be performed before randomization and after 24 months of TPTD (Table 1). A quadruple labeled transiliac crest bone biopsy will be performed at 3 months for both Group A and B. Eli Lilly & Company will provide TPTD and placebo but will supply no other funding. After 24 months of treatment in either Group A or B, all women will be offered three choices for follow up: the subjects can A) continue to to be followed for 12 months off TPTD B) choice to leave the study and be treated clinically using an anti-resorptive medication to maintain gains in bone density after treatment with TPTD, or C) join a new study to maintain gains in bone density after treatment. The new study is currently in the design phase and funding phase and precise details are not yet available.

Statistical Analysis Plan

2.A. Statistical Analysis Plan Our aims in this protocol are as follows:

Aim 1: To establish the efficacy and safety of 6 months of TPTD versus placebo in premenopausal women with IOP

Aim 2: To determine the effect of 3 months of TPTD on bone remodeling at the tissue level and the extent to which baseline and 3 month bone remodeling predicts response to TPTD in premenopausal women with IOP.

Aim 3: To determine the extent to which 12 and 24 months of TPTD improves areal and volumetric BMD, bone microarchitecture and strength (stiffness) compared to baseline measures in premenopausal women with IOP

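### The stated power of over 90% for the primary lumbar spine BMD comparison does not follow from its own inputs, which give about 77% at 28:12 and 72–79% if 10% of the 40 women drop out

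*Combined protocol and SAP*

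**What the plan says.** The power statement for the primary efficacy endpoint is in section 2.B, Aim 1: "outcome correlation with baseline covariates of 0.3, we will have >90% power to detect a difference of" 3.7 ± 3.3% versus 0.8 ± 2.9%. The introduction to 2.B gives the sample: "Our power estimates are based upon 40 women randomized to TPTD or placebo (28:12) with data for analysis, assuming a 10% drop-out", with alpha 5%.

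The other inputs are elsewhere:

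- Section 2.A sets the test: "Inferential testing will use a 5% two-tailed type I error rate".
- Section 2.A, Aim 1, defines the model as an ANCOVA of the two groups "with adjustment for the following continuous baseline variables LS aBMD (g/cm^2), age (years) and weight (kg", which is three covariates.
- Section 1, describing the randomization error, gives the intended design: "Subjects (n=40) should have been randomized 28:12, active Teriparatide to placebo, for 6 months".
- Section 2 gives the current design: "Forty-one subjects will be assigned to TPTD (Group A; n=28) or placebo (Group B; n=13". Section 2.B still uses 28:12.

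The placebo mean and SD are described in 2.B as a "placebo estimate based on interpolation from our preliminary data at 12 months". Section 11 (Potential Risks) reports the same lumbar spine figure, 0.8 ± 2.9%, for 18 women with IOP followed for an average of 4 years.

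**The concern.** A difference of 2.9 points against SDs near 3.2 is a standardized effect of about 0.9. With only 12 women in the smaller arm, and a covariate correlation of 0.3 that removes only 9% of the variance, power above 90% looks too high.

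This is the only Aim 1 comparison for which the plan claims adequate power. For the secondary BMD sites section 2.B says "we will not have sufficient power to detect between groups differences in these measures at 6 months", and it concedes low power for the safety comparisons as well. The sample size justification for Aim 1 therefore rests on this one figure. If it is overstated, a non-significant primary result would be read as stronger evidence against the planned effect than the design can supply.

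**Working it through.** **Inputs.** Difference 3.7 − 0.8 = 2.9 points, SDs 3.3 and 2.9, correlation 0.3 (2.B, Aim 1); 28:12 (2.B); two-sided 5% and three covariates (2.A).

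**Attempt to reproduce the stated figure at 28:12**

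1. Pooled SD = √[(27 × 3.3² + 11 × 2.9²) / 38] = 3.189.
2. Residual SD after covariates = 3.189 × √(1 − 0.3²) = 3.042.
3. Noncentrality = (2.9 / 3.042) × √(28 × 12 / 40) = 2.763.
4. Degrees of freedom = 40 − 2 − 3 = 35.
5. Two-sided noncentral-t power = **76.6%**.

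The figure of over 90% is not reproduced.

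**Other allocations, same method**

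- If 40 is the number randomized and 10% are lost, 28 × 0.9 = 25.2 and 12 × 0.9 = 10.8, so 25:11. Noncentrality 2.636, power 72.4%.
- Current 28:13: noncentrality 2.846, power 79.1%.

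**Sensitivity to method.** The SDs were pooled, averaged as variances, or kept separate by arm, each with a t and a normal calculation. Entries are power in %, with 0.3 read as the correlation (R² = 0.09).

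| Analysed | Pooled t | Pooled z | Mean-variance t | Mean-variance z | Unequal-variance t | Unequal-variance z |
|---|---|---|---|---|---|---|
| 28:12 | 76.6 | 78.9 | 78.7 | 81.0 | 80.8 | 82.9 |
| 25:11 | 72.4 | 75.0 | 74.5 | 77.2 | 76.7 | 79.2 |
| 28:13 | 79.1 | 81.2 | 81.0 | 83.0 | 82.8 | 84.8 |

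No cell reaches 90%. Two simulations of the three-covariate ANCOVA (40,000 runs each, multiple correlation 0.3, unequal SDs, random covariates) gave slightly less than the formulas: 73.6% and 74.0% at 28:12, 69.1% and 69.2% at 25:11, 76.8% and 76.5% at 28:13.

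**Sensitivity to the meaning of 0.3** (range over the same six calculations)

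| Reading | 28:12 | 25:11 | 28:13 |
|---|---|---|---|
| Correlation 0.3 (R² = 0.09) | 76.6–82.9 | 72.4–79.2 | 79.1–84.8 |
| Three independent covariates at 0.3 each (R² = 3 × 0.09 = 0.27) | 85.1–90.2 | 81.3–87.3 | 87.1–91.5 |
| R² = 0.30 | 86.5–91.3 | 82.9–88.6 | 88.4–92.6 |

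At 28:12, the allocation on which the claim is based, only the unequal-variance normal calculation passes 90% under the last two readings. At 25:11 none does.

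**What 90% would need at 28:12** (pooled SD, t): a difference of 3.50 points instead of 2.9, or R² = 0.375, a multiple correlation of about 0.61 instead of 0.3.

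**Sensitivity to the placebo mean.** These values are assumed, with both SDs unchanged, correlation 0.3, pooled SD and t.

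| Placebo change | Difference | 28:12 | 25:11 | 28:13 |
|---|---|---|---|---|
| 0.8% (stated) | 2.9 | 76.6 | 72.4 | 79.1 |
| 0.4% | 3.3 | 86.4 | 82.8 | 88.3 |
| 0.2% | 3.5 | 90.0 | 86.9 | 91.7 |
| 0.1% | 3.6 | 91.5 | 88.7 | 93.0 |

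**The case against.** The strongest counter-argument is that the shortfall depends on a placebo input that is itself in doubt. If 0.8% is a change over 4 years, as section 11 has it, a linear 6-month change would be 0.8 × 0.5 / 4 = 0.1%. The difference would then be 3.6 points and power 91.5–95.1% at 28:12 across the six calculations. The printed 0.8% could be the mistake and the stated power roughly right. This stands as a reason to reconcile sections 2.B and 11. It does not rescue the statement as written, which names 0.8 ± 2.9% as the input. It also assumes linear change and that both SDs carry over to 6 months, neither of which the documents support.

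Second, the text speaks of covariates in the plural, so 0.3 might apply to each of three. That is a fair reading and narrows the gap to 0–5 points at 28:12. It needs the covariates to be mutually independent, which the plan does not say, and five of the six calculations still fall below 90%.

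Third, 77% is the lowest of the six formula values. That is true, but it is the calculation closest to the planned ANCOVA, and the simulations fall below it.

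Fourth, the sample size sentence can be read as 40 evaluable women. The 72–79% range applies only if 40 is the number randomized; the 28:12 figures cover the other reading.

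Two smaller points also stand. The planned analysis is of change in g/cm², while the power inputs are percent changes, so no figure here is exactly the power of the planned test. And the study describes itself as exploratory: a wrong power statement does not bias the eventual estimate.

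**Conclusion.** The concern holds. On the stated means, SDs, correlation, model, alpha and allocation, power is about 77% at 28:12 (77–83% by formula), 7 to 13 points below the 90% threshold and well outside rounding. The chance of missing the planned difference is about 23% at 28:12, 28% at 25:11 and 21% at 28:13 (pooled SD, t), against under 10% as claimed.

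That the claim does not follow from its inputs is firm. The exact replacement figure is conditional on three things the plan leaves unclear: whether 0.3 is a correlation or R-squared, whether 40 is randomized or evaluable, and whether 0.8 ± 2.9% comes from 12 months or 4 years. The documents do not show which description of the placebo figure is right.

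**What to change.** In section 2.B, Aim 1:

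1. Replace the figure of over 90% with the power the stated inputs deliver: about 77% at 28:12, about 72% if 10% of the 40 drop out (25:11), and about 79% at the current 28:13. A drop-out figure for 28:13 should be added on the same basis: 28 × 0.9 = 25.2 and 13 × 0.9 = 11.7, so 25:12, which gives about 75% (75.2–81.4% by method).
2. State whether 0.3 is a multiple correlation, a per-covariate correlation or R-squared, and how the two SDs were combined.
3. State whether 40 is the number randomized or the number with data for analysis.
4. Reconcile sections 2.B and 11 on the source and time base of the placebo mean and SD, and recompute if either changes.

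If the sponsor used other inputs, printing them so that the figure can be reproduced would equally settle the point. The cost is wording in one section and a less favourable stated power. Enrolment, the analysis model and conduct are unaffected.

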c. Hypercalcemia, Hyperuricemia and Hypercalciuria: Hypercalcemia and mild increases in serum uric acid are known side effects of PTH, although not very common at the FDA-approved 20 mcg/day dose that we will use. A post-hoc analysis of two prospective randomized clinical trials involving 1,637 postmenopausal women and 2,437 men found that urinary calcium excretion increases by an average of 32 mg/d on the 20 mcg dose of TPTD⁶⁷. [name], the Study Monitor, will monitor pre-dose serum calcium and uric acid and urinary calcium excretion at 1 to 6-month intervals to determine the incidence of these abnormalities in our study participants. We will exclude subjects with hypercalcemia (fasting serum calcium >10.2 mg/dl) and hypercalciuria (>300 mg/g creatinine) at baseline.

For subjects in the placebo group during months 0-6, there may be a risk of bone loss. However, Peris et al. reported a retrospective analysis of 16 women with IOP, managed with calcium, vitamin D and increased physical activity⁶⁸ They documented small increases in BMD and no fractures over an average 3 years of observation, supporting the safety of a placebo-controlled design. We have longitudinal BMD data in 18 women with IOP followed on calcium (1000-1500 mg/day) and vitamin D (800-1000 IU/day) for an average of 4 years. LS BMD increased by $0.8 \pm 2.9\%$, while there were slight decreases at the FN (-1.2 ± 5.3%), TH (-0.5 ± 3.4%) and 1/3 Radius (-2.4 ± 2.8%). None of the decreases were statistically significant. Thus, we do not expect major declines in BMD in the women randomized to placebo for the first 6 months and in any case, all subjects will receive teriparatide after the first 6 months.

2) Radiation

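### The placebo lumbar spine change behind the primary power statement (0.8 ± 2.9%) is printed with two incompatible time bases, so the planned 6-month contrast and its power cannot be pinned down.

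*Combined protocol and SAP*

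**What the plan says.** Section 2.B (Power and Sample Size, AIM 1, primary efficacy outcome) sets LS BMD change at 6 months to 3.7 ± 3.3% on teriparatide and 0.8 ± 2.9% on placebo, a contrast of 2.9 points. It claims that "we will have >90% power to detect a difference of" this size, with a covariate correlation of 0.3. It gives the origin of the placebo figure as "placebo estimate based on interpolation from our preliminary data at 12 months". The opening of 2.B names the teriparatide pilot as the basis of the power calculations and uses 40 women split 28:12.

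Section 11 (Potential Risks), arguing that six months of placebo is acceptable, describes 18 women with idiopathic osteoporosis taking calcium and vitamin D. The text reads "for an average of 4 years. LS BMD increased by" and then gives 0.8 ± 2.9%: the same site, mean and SD as in 2.B.

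Section 2.A tests the primary outcome by ANCOVA and adds: "Inferential testing will use a 5% two-tailed type I error rate". Section 2 and Visit 3 in Section 3.A give the current allocation as 28:13.

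**The concern.** One mean and SD cannot be both a 6-month value interpolated from 12-month data and the change seen over about 4 years. A coincidence is unlikely: both numbers agree to the printed decimal, and interpolation from a longer window would be expected to change at least the mean. The documents print no 12-month LS figure for untreated women. The pilot named in 2.B treated its women with teriparatide, so it describes no placebo group. The Section 11 cohort is the only untreated LS dataset from the study team that carries figures.

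At stake is whether the primary power statement can be checked. The time base decides the expected placebo mean, and so the contrast. It also bears on the SD, because the spread of change over about 4 years need not be the spread at 6 months.

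**Working it through.** **Inputs.** From 2.B: teriparatide mean 3.7, SD 3.3; placebo mean 0.8, SD 2.9; r = 0.3; allocation 28:12; 10% drop-out. From 2.A: two-sided 5% and three baseline covariates. From Sections 2 and 3.A: 28:13. From Section 11: average follow-up of 4 years.

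**Step 1: placebo mean at 6 months under each time base (linear change assumed).**
- As printed: 0.8; contrast 3.7 − 0.8 = 2.9.
- If 0.8% is a 12-month or per-year change: 0.8 × 0.5 = 0.4; contrast 3.7 − 0.4 = 3.3.
- If 0.8% is a cumulative 4-year change: 0.8 × 0.5/4 = 0.1; contrast 3.7 − 0.1 = 3.6, which is 3.6/2.9 = 1.24 times the printed one.

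**Step 2: method.** Pooled SD s = √{[(n₁−1)·3.3² + (n₂−1)·2.9²]/(n₁+n₂−2)}. Residual SD = s·√(1−0.3²). SE = residual SD·√(1/n₁+1/n₂). Power comes from the noncentral t distribution with noncentrality contrast/SE and n₁+n₂−5 degrees of freedom (two groups, three covariates).

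**Step 3: the plan's own figure, at 28:12.**
- s = √[(27·10.89 + 11·8.41)/38] = 3.19.
- Residual SD = 3.19 × 0.954 = 3.04.
- SE = 3.04 × √(1/28+1/12) = 1.05.
- Noncentrality = 2.9/1.05 = 2.76 on 35 df, giving power 76.6% (78.9% by normal approximation).

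The stated figure above 90% is not reproduced on this literal reading.

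**Step 4: the same calculation for each contrast and allocation.** 25:11 is 28:12 after 10% drop-out, rounded.

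| Allocation | Contrast 2.9 | Contrast 3.3 | Contrast 3.6 |
|---|---|---|---|
| 28:12 | 76.6% | 86.4% | 91.5% |
| 28:13 (current) | 79.1% | 88.3% | 93.0% |
| 25:11 | 72.4% | 82.8% | 88.7% |

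**Step 5: sensitivity to the SD.** The documents give no 6-month placebo SD. With an assumed placebo SD of 1.0 to 2.0%, contrast 3.6 and r = 0.3, power at 28:12 is 96.3% to 94.6%.

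**Step 6: sensitivity to linearity.** An early gain followed by a plateau could put the 6-month placebo mean anywhere from 0.1% to 0.8%, so the contrast could lie anywhere from 2.9 to 3.6 points.

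**The case against.** The best reply is that this may be only a reporting slip. A placebo mean of 0.1% gives about 92% at 28:12, which agrees with the stated figure above 90%; 0.8% gives about 77%. The authors may have interpolated correctly, calculated with the result, and printed the raw value. That stands as a real possibility. It is not proof, because power above 90% can also be reached by other routes, for example by reading 0.3 as a squared multiple correlation and using an unequal-variance normal approximation (about 91% at 28:12 with the printed contrast).

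Three further points also stand. Section 11 does not say whether 0.8% is cumulative or annualised, and the error may lie in its follow-up time. The likely correction enlarges the contrast. And no success margin, futility boundary or interim efficacy analysis uses the planned contrast; the primary outcome is judged by ANCOVA at two-sided 5%.

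A reader might therefore infer too much in three ways: that a 4-year change was certainly used with no interpolation, that this discrepancy leaves the trial underpowered, or that the 2.9-point contrast is the yardstick for the result. The documents support none of these. They do not settle which section is wrong or which value entered the calculation; the correction, if anything, raises power; and the planned contrast has no role in the test.

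What the reply does not remove is the contradiction itself, or the fact that the power statement cannot be verified while it remains.

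**Conclusion.** The inconsistency holds: one figure, two time bases, and at least one description is wrong. The planned 6-month contrast is 2.9 points as printed, about 3.3 if 0.8% is a 12-month or per-year change, and about 3.6 if it is cumulative over 4 years. Power differs by about 15 percentage points between the extremes at 28:12 (77% to 92%) and by about 14 at 28:13 (79% to 93%). The scaled values assume linear change; all the main power figures assume SDs of 3.3 and 2.9 and a literal r = 0.3.

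That the 2.B figure comes from the Section 11 cohort is a strong inference, not an established fact. The direction is benign, and neither the validity of the primary test nor enrolment is in question. What needs repair is the documented basis of the primary power statement. That the printed inputs give about 77% on a literal reading is a separate matter, but it cannot be resolved until this input is settled.

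**What to change.** 1. In Sections 2.B and 11, state the source of 0.8 ± 2.9%, its follow-up time, and whether it is cumulative or annualised, so that the two agree.
2. In 2.B, replace it with a 6-month placebo mean and SD. Use early scans from the 18-woman cohort if they exist (the protocol gives no scan schedule for it); otherwise use each woman's annualised change, with a stated range for mean and SD.
3. Restate the expected 6-month contrast and the power at 28:13, making clear what the 0.3 denotes and whether the numbers are before or after drop-out.
4. If the 4-year follow-up is the error, correct Section 11 and still restate the 6-month value in 2.B.

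The cost is a small reanalysis of the cohort data and a text correction. Section 2.A already says that the analysis plan will be modified for Aim 1 because of the adaptive randomization, so the change can go in the same revision. Enrolment, procedures and the primary test stay as they are.
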